### **OUTCOME ASSESSMENTS**

- Visual Analog Scale (VAS) Degree of Pain Rating
- Linear Range of Motion (ROM)
- Subject Satisfaction with Study Outcome Rating
- Adverse Events Evaluation

## **POST-PROCEDURE ACTIVITIES**

The post-procedure evaluation phase of this study will commence immediately following completion of the procedure administration phase evaluations and will last for 2 days (48 hours).

The post-procedure outcome assessments will be recorded by the subject in his or her own home on forms provided by the test site. The subject will be instructed on when and how to complete the forms and how to return them to the test site prior to leaving the test site on the procedure administration day.

## **24 HOURS AND 48 HOURS POST-PROCEDURE EVALUATIONS**

The subject will be required to record the following at home on the forms provided by the test site at 24 hours and again at 48 hours after completion of the procedure administration phase at the test site.

### **OUTCOME ASSESSMENTS**

- Visual Analog Scale (VAS) Degree of Pain Rating
- Linear Range of Motion (ROM)
- Subject Satisfaction with Study Outcome Rating
- Adverse Events Evaluation

## **ADVERSE EVENTS**

At each evaluation point throughout the clinical study, and at any other time throughout the duration of the clinical trial that is necessary, any and all potential adverse events reported by a subject or observed by an investigator will be recorded on the case report form, and subsequently evaluated by a suitably qualified independent reviewer for determination of relationship to the study treatment and whether or not any corrective action needs to be taken. All potential adverse events recorded will be appropriately reported to the governing IRB, as applicable.

It is unlikely and not expected that any adverse events will result from implementation of this clinical study protocol. Prior clinical trials using low level laser light have not typically yielded any adverse events or reactions. However, potential adverse events that may feasibly occur from application of the Erchonia® EVRL include, but are not necessarily limited to: skin irritation, discoloring, rash, indentations and infection.

## **PRIVACY AND CONFIDENTIALITY**

Records for each subject in this clinical study will be maintained in separate files in a locked filing cabinet at the respective test site. The investigator at the test site will be responsible for ensuring that all records for a subject pertaining to his or her participation in the clinical study are stored in that subject's file at all times other than when information is being recorded on them.

Copies of all of the subject case report forms will be made and supplied to Regulatory Insight, Inc. and Erchonia Corporation. Regulatory Insight, Inc. and Erchonia Corporation will maintain these copies in a separate clinical study file that is kept in a locked filing cabinet at their respective premises. The original records will be maintained at the respective test sites.

Subjects' identities will be kept confidential by assigning each subject a subject ID upon acceptance into the study. The subject ID will comprise the investigator's two initials (first and last name initials) and a three-digit number that will be based upon the subject's order of entry into the clinical study. Each test site will be assigned a unique range of numbers. Test site #1 will be assigned numbers 001 to 100 (Subject ID RS001 to RS100). Test site #2 will be assigned numbers 101 to 200 (Subject ID AC101 to AC200). For example, the eighth subject to be enrolled at test site #2 would have a subject ID of AC108. Neither the study Sponsor nor Regulatory Insight, Inc. will receive any additional identifying information about a subject and will therefore have no way of linking a Subject ID to a particular subject and his or her results.

## **STATISTICAL ANALYSIS**

### **PRIMARY EFFICACY OUTCOME MEASURE: CHANGE IN SUBJECT SELF-REPORTED VAS PAIN RATING FROM BASELINE TO STUDY ENDPOINT**

Primary efficacy outcome measure for this clinical study is the proportion of subjects who meet the study individual success criteria.

#### Individual Subject Success Criteria

Individual subject success criteria is defined as a 30% or greater decrease in self-reported VAS pain rating at study endpoint relative to baseline.

#### Overall Study Success Criteria

Overall study success criteria is defined as at least  $65\% \pm 5\%$  of subjects meeting the study individual success criteria.

The clinical relevance and justification of the individual and overall study success criteria is as follows:

- This study is a non-inferiority study, such that the research hypothesis is that the red/violet diode combination therapy with the Erchonia® EVRL is either equivalent to or superior to the red diode only therapy with the Erchonia® EVRL in effecting a clinically meaningful reduction in neck and shoulder pain of musculoskeletal origin, based upon the data attained from the red diode only clinical trial conducted in 2001 whose results successfully supported 510(k) clearance of application of the EVRL in red diode mode only for the identical indication being sought through the results of this clinical trial.
- The individual subject success criteria in this clinical study is identical to that of the comparative reference study.
- The overall study success criteria in this clinical study is based on the actual proportion of individual subject successes attained during the comparative reference trial for the active red diode treatment group, of 65%. The  $\pm 5\%$  is the selected equivalence margin ( $\delta$ ), the maximally clinically acceptable difference for which the range of values (60% to 70%) for which the efficacies are “close enough” to be considered equivalent.
- Non-inferiority will be established if the proportion of subjects who attain the individual subject success criteria is no more than 5% less than the reference subject group (no less than 60%).

#### Hypotheses

- *Null Hypothesis:* Treatment application of the Erchonia® EVRL in simultaneous dual-diode mode (red and blue/violet) is inferior to treatment application of the Erchonia® EVRL in red diode mode only in reducing neck and shoulder pain of musculoskeletal origin.
- *Alternative Hypotheses:* Treatment application of the Erchonia® EVRL in simultaneous dual-diode mode (red and blue/violet) is NOT inferior to treatment application of the Erchonia® EVRL in red diode mode only in reducing neck and shoulder pain of musculoskeletal origin.

#### Evaluation Time Point

Study endpoint evaluation is immediately following the study single procedure administration. Study success will be analyzed at study endpoint relative to baseline.

The study endpoint evaluation is identical to that in the reference comparative study.

## PRIMARY EFFICACY OUTCOME STATISTICAL EVALUATION

- Primary analysis of efficacy will be according to intent to treat (ITT) analysis (including all enrolled subjects) supported by per protocol (PP) analysis (including only subjects who completed the study according to the full protocol). Non-inferiority will be established if both the ITT and PP analyses agree.
- Missing data for the ITT population will be handled through Last Observation Carried Forward (LOCF): by carrying forward the last recorded observation to fill in the subsequent missing value.
- Statistical evaluation of study success will be conducted through the two one-sided test (TOST) procedure. Non-inferiority is established at the  $\alpha=0.05$  significance level if the lower limit of the  $(1-2\alpha)*100\%$  confidence interval ( $(1-2*0.05)*100\% = 90\%$  confidence interval) for the difference in efficacies (dual-diode versus red diode only) is above  $-\delta$  (60%).

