## **PROCEDURE ADMINISTRATION PHASE EVALUATIONS: STUDY ENDPOINT**

Within 3 minutes of completion of the procedure administration phase, study endpoint evaluation will occur.

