## SECONDARY EVALUATIONS

The following secondary evaluations will be performed in support of the primary efficacy evaluation:

- TOST analysis of the difference in the mean change in VAS levels from baseline to endpoint between the dual-diode and red only diode treatment administration groups.
- Descriptive analysis of the change in mean VAS ratings across all study evaluation points (baseline, endpoint, 24 hours and 48 hours post-procedure).
- Analysis of change in linear ROM measurements across study evaluation points.
- Descriptive analysis of categorical subject satisfaction with study outcome ratings.

Secondary evaluation will be conducted within the dual-diode treatment group and between the dual-diode and red diode only treatment groups.

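### The single LOCF rule has no stated scope: if it is applied to the 24/48 h VAS course, it fills missing home scores with the score taken minutes after treatment

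*Combined protocol and SAP*

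**What the plan says.** Under Primary Efficacy Outcome Statistical Evaluation: "Missing data for the ITT population will be handled through Last Observation Carried Forward (LOCF"), explained as "by carrying forward the last recorded observation to fill in the subsequent missing value". No visit is named.

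The primary outcome is immediate. Individual success is a "30% or greater decrease in self-reported VAS pain rating at study endpoint relative to baseline", and the timing is fixed by "Within 3 minutes of completion of the procedure administration phase, study endpoint evaluation will occur". The Evaluation Time Point section adds: "Study success will be analyzed at study endpoint relative to baseline".

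The later VAS scores come from home. Under Post-Procedure Activities: "The post-procedure outcome assessments will be recorded by the subject in his or her own home on forms provided by the test site". They are used under Secondary Evaluations, which lists "Descriptive analysis of the change in mean VAS ratings across all study evaluation points", naming baseline, endpoint, 24 h and 48 h. That section plans its evaluations both within the dual-diode group and against the red-diode group. It gives no missing-data rule and no sensitivity analysis.

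**The concern.** Qualification, baseline, treatment and the primary VAS all fall on one day, with the endpoint score taken minutes after treatment. Few primary scores should be missing. The 24 h and 48 h forms, completed and returned by the subject, are where gaps are most likely, and they are the only later VAS values that a carry-forward rule could fill. Read plainly, a rule for the whole ITT population would therefore do most of its work there.

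What it would insert is the immediate post-treatment score, so it assumes that relief persists in anyone who does not return a form. The indication sought is temporary relief, which makes that a poor default. If some subjects fail to respond because their pain came back, they would be counted as still relieved, and the mean VAS course would suggest a longer-lasting effect than was observed. Imputed scores would also be treated as if measured, so the uncertainty from imputing them is ignored.

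**Working it through.** The plan gives no dropout rate and no expected 24/48 h value, so there is no design figure to reproduce.

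**Inputs**
- Sample size 43 (Sample Size).
- Reference active-arm VAS 60.2 before and 31.2 after treatment (Primary Endpoint results of the reproduced publication). Check: 60.2 − 31.2 = 29.0, as printed.
- Missing count, by assumption: Table 3 of that publication (rescue medication) prints denominators of 35 or 36 per arm out of 43. This gives 43 − 36 = 7 (16.3%) or 43 − 35 = 8 (18.6%). The active arm is printed as 35 at both times.

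**Step 1: the primary endpoint.** A missing endpoint VAS takes the baseline value. Change = (baseline − baseline)/baseline = 0%, below 30%, so the subject is a non-responder. With a true rate of 65.1% and m endpoint scores missing at random, the ITT rate is 0.651 × (43 − m)/43: 63.6% for m = 1, 62.1% for m = 2, 59.0% for m = 4. The rule lowers the primary result; it does not inflate it.

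**Step 2: what is carried to 24 and 48 h, if the rule reaches that far**

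| Home forms returned | Value used at 24 h | Value used at 48 h |
|---|---|---|
| 24 h only | observed | 24 h score |
| 48 h only | 3-minute score | observed |
| neither | 3-minute score | 3-minute score |

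**Step 3: size.** Where the 3-minute score is carried, the mean VAS is understated (relief overstated) by (m/43) × r, where r is the mean rise in the missing subjects after the immediate score.

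| Rise r in missing subjects | 7 of 43 missing | 8 of 43 missing |
|---|---|---|
| −10 (further improvement) | −1.6 | −1.9 |
| 0 | 0 | 0 |
| 10 | 1.6 | 1.9 |
| 20 | 3.3 | 3.7 |
| 29.0 (back to baseline) | 4.7 | 5.4 |

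The bound is 7/43 × 29.0 = 4.7 and 8/43 × 29.0 = 5.4 points, or 16% to 19% of the 29.0-point gain. For 48 h it assumes that both forms are missing.

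**Step 4: would another method do better?** Take 8 missing subjects, with all 43 at 60.2 before and 31.2 just after treatment.

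| Returners' rise | Missing subjects' rise | True mean | LOCF | Observed only | Missing set to baseline |
|---|---|---|---|---|---|
| 0 | 29.0 | 36.6 | 31.2 | 31.2 | 36.6 |
| 10 | 10 | 41.2 | 39.3 | 41.2 | 44.7 |
| 10 | 29.0 | 44.7 | 39.3 | 41.2 | 44.7 |

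First row: true mean = (35 × 31.2 + 8 × 60.2)/43 = 36.6. Third row: LOCF = (35 × 41.2 + 8 × 31.2)/43 = 39.3. Observed data improve on LOCF when returners also rebound. In the first row they share its full 5.4-point error, and a mixed model that assumes missing at random would give about the same. Only the return-to-baseline analysis covers that case.

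**The case against.** The strongest reply is about scope. The LOCF bullet sits under the primary heading, between the analysis-set bullet and the TOST bullet, and the sponsor may have meant it for the primary endpoint only. That stands: its reach to 24/48 h is inferred. But the sentence covers the ITT population without limit and the secondary section is silent, so the text leaves both readings open.

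A reader might infer that the rule certainly overstates durability. The documents do not show this. The reference publication reports no significant difference between immediate, 24 h and 48 h ratings, and its introduction says that relief held for 24 hours in most subjects of an earlier trial. That does not establish persistence either: the reference study itself imputed by LOCF, rescue medication was used, and the same paragraph reports no active-versus-sham difference at 24 and 48 h after a 24.1-point gap immediately. The direction depends on what happens in non-returners, which is unknown.

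A reader might also infer that 16–19% of home forms will be lost. The plan gives no such rate. Table 3 counts rescue-medication responses, its percentages fit denominators anywhere from 33 to 36, and the publication says that all 86 enrolled subjects completed.

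Nor can bias in favour of the dual-diode group be inferred. With LOCF in both groups, the net effect depends on differences in missingness and rebound, and has no fixed sign. Likewise, standard deviations need not be too small: if returners rebound while carried values stay low, the spread can widen.

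**Conclusion.** The point holds as an unclear rule with a poor default, conditional on its being applied to the 24/48 h VAS course. In that case the overstatement of mean relief is 0 with no rebound and 4.7 to 5.4 VAS points with full return to baseline. This assumes 7 to 8 of 43 missing, an immediate gain of 29.0 points as in the reference active arm, and the 3-minute score as the value carried.

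The primary result is not inflated, no success criterion uses 24/48 h data, and the affected VAS analysis is descriptive. Severity is minor.

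**What to change.** 1. Limit the LOCF sentence to the primary endpoint and reword it so that a missing endpoint VAS counts as a non-response. This leaves the primary analysis unchanged.
2. For VAS at 24 and 48 h, report observed n, mean and SD, and do not carry the immediate score forward.
3. For any between-group statement at 24 or 48 h, use a mixed model for repeated measures with baseline VAS, handling missing data alike in both groups where subject-level reference data allow.
4. Add one sensitivity analysis that sets missing 24/48 h VAS to baseline, since neither observed-case reporting nor the mixed model corrects for non-return caused by returning pain.

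The cost is a few lines of SAP text and a little more analysis. Conduct and sample size do not change. The 24/48 h figures may look slightly less favourable.

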## SECONDARY EVALUATIONS

The following secondary evaluations will be performed in support of the primary efficacy evaluation:

- TOST analysis of the difference in the mean change in VAS levels from baseline to endpoint between the dual-diode and red only diode treatment administration groups.
- Descriptive analysis of the change in mean VAS ratings across all study evaluation points (baseline, endpoint, 24 hours and 48 hours post-procedure).
- Analysis of change in linear ROM measurements across study evaluation points.
- Descriptive analysis of categorical subject satisfaction with study outcome ratings.

Secondary evaluation will be conducted within the dual-diode treatment group and between the dual-diode and red diode only treatment groups.

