#### Sample Size

There will be 43 qualified subjects enrolled in this study.

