## COVARIATE ANALYSIS

The impact of the following potential covariates on study outcome will be evaluated:

- Baseline VAS rating
- Age
- Gender
- Ethnicity
- Etiology

Analysis of results will be performed by individual test site and pooled across test sites.

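### The secondary TOST on mean VAS change has no margin in VAS units, no stated decision rule and no stated adjustment, so a margin chosen later can decide its verdict.

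*Combined protocol and SAP*

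**What the plan says.** The first bullet under Secondary Evaluations is a "TOST analysis of the difference in the mean change in VAS levels from baseline to endpoint", comparing the dual-diode and red-only groups. It names no margin, significance level, model or covariate.

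The related text elsewhere is:

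- **Primary Efficacy Outcome Statistical Evaluation.** "Statistical evaluation of study success will be conducted through the two one-sided test (TOST) procedure". The decision is then read from one side only: "Non-inferiority is established at the $\alpha=0.05$ significance level if the lower limit of the" 90% interval lies above the negative margin.
- **Overall Study Success Criteria.** The 5% around the 65% responder rate "is the selected equivalence margin", described with a range of 60% to 70%. The research hypothesis is that dual-diode therapy "is either equivalent to or superior to the red diode only therapy". Expected Results likewise accepts comparable or better pain reduction.
- **Covariate Analysis.** "Baseline VAS rating" heads a list with age, gender, ethnicity and etiology, whose impact on outcome will be evaluated. No model is named and there is no link to the VAS TOST.
- **Subject Group, Blinding and Randomization.** The red-only data come from the 2001 study, the comparison is not randomized, and the statistician receives both data sets labelled only as groups A and B.
- **Sample Size.** "There will be 43 qualified subjects enrolled in this study".

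**The concern.** A TOST gives no answer until a margin is set. The one margin in the plan is on the responder-proportion scale and cannot be carried over to millimetres of VAS. The reference VAS result is already printed in the protocol, so a margin chosen later is chosen with at least half of the data known. Masking the group labels gives limited protection, because the published reference means could identify the group.

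Two further gaps compound this. The bullet does not say whether the primary's lower-limit rule carries over or whether both limits count, and the two rules give opposite answers for a better device. The control is historical and baseline VAS is recorded in both studies, yet nothing says that the comparison will be adjusted for it. At stake is whether the supporting analysis can be read as confirmation of the primary result.

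**Working it through.** **Figures in the documents.** The confidence level follows from the primary's alpha: (1 − 2 × 0.05) × 100% = 90%. The reference active arm changed by 60.2 − 31.2 = 29.0 points and the sham arm by 60.0 − 55.1 = 4.9, a difference of 24.1. Responders in the active arm were 28/43 = 65.1%. All reproduce. There is no stated margin, SD or power for the VAS test to reproduce.

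**Assumed input.** The SD of VAS change is not given, so I take 12 to 30 mm. A rough guide to the upper part of that range: if percent change is normal with mean 29.0/60.2 = 48.2% and 65.1% of subjects reach 30%, the SD is (48.2 − 30)/0.388 = 46.9%, or about 0.469 × 60.2 = 28 mm.

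**Half-width of the 90% interval**, 43 v 43: 1.645 × SD × √(2/43).

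| SD (mm) | 12 | 15 | 20 | 25 | 30 |
|---|---|---|---|---|---|
| Half-width (mm) | 4.3 | 5.3 | 7.1 | 8.9 | 10.6 |

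With an observed difference of 0, the two decision rules coincide and the test passes when the margin exceeds the half-width. A 5 mm margin passes for SD below about 14 (5/(1.645 × √(2/43)) = 14.1) and fails above it. A 12 mm margin, about half of 24.1, passes throughout.

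**Probability of passing with no true difference** (simulation, pooled t, 200,000 runs per case; the t-based half-widths are 7.17 and 10.04 mm):

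| SD | Rule | Margin 5 | Margin 10 | Margin 15 |
|---|---|---|---|---|
| 20 | both limits | 0.000 | 0.487 | 0.928 |
| 20 | lower limit only | 0.313 | 0.745 | 0.965 |
| 28 | both limits | 0.000 | 0.041 | 0.587 |
| 28 | lower limit only | 0.206 | 0.501 | 0.794 |

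The margin moves the answer under either rule.

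**A better device.** Count extra pain reduction with dual-diode as positive. With a true advantage of 10 mm, SD 20 and margin 10, the both-limits rule passes with probability 0.049 and the lower-limit rule with 0.998. With an advantage of 20 mm the figures are 0.000 and 1.000. An observed advantage of 20 mm at SD 20 has a 90% interval of 12.8 to 27.2: it fails the both-limits rule at any margin up to 27 and passes the lower-limit rule at any margin.

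**What baseline adjustment saves.** With baseline SD b, endpoint SD e and correlation r, the change-score variance is b² + e² − 2rbe, which equals e²(1 − r²) + (b − re)². The ANCOVA residual variance is e²(1 − r²). The saving is therefore never negative in large samples when the two groups have similar baseline means. Both studies required VAS of at least 50 at entry, which restricts the baseline spread but not the endpoint spread. Assume b of 8 to 15, e of 20 to 25 and r of 0.3 to 0.7:

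- b = 10, e = 20, r = 0.5: 300/300 = 1.00, saving 0%.
- b = 15, e = 20, r = 0.3: 364/445 = 0.82, saving 18%.
- b = 8, e = 25, r = 0.7: 318.75/409 = 0.78, saving 22%.

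If baseline means differ by d baseline SDs, the ANCOVA variance is multiplied by about 1 + d²/4, for example 1.06 at d = 0.5.

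**The case against.** The strongest reply is that the plan shows how it uses the term TOST. In the primary analysis it names TOST and then decides on the lower limit alone, the hypotheses are one-sided, and superior results count as success. The secondary evaluations are offered in support of the primary, so the natural reading carries the lower-limit rule over, and under that rule a better device passes. A reader might infer that the VAS analysis is definitely a two-sided equivalence test that a clearly better device must fail. The documents do not support that as fact. What stands is ambiguity: the rule is not restated for VAS, the margin is called an equivalence margin with a symmetric range, and a lower-limit test needs to know which group is new while the statistician is masked to that.

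A reader might also call the comparison unadjusted. That goes too far: a covariate evaluation including baseline VAS is planned. But it has no model and is not tied to this test. A large precision gain from ANCOVA is tempting too; a saving of 15% to 35% follows only if baseline and endpoint variances are equal, which the entry floor makes unlikely. In non-randomized groups, change scores and ANCOVA rest on different assumptions, and neither is automatically less biased.

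Nor can a margin produce any verdict at will: for a given result and rule, only margins beyond the relevant limit or limits pass. Finally, study success rests on the responder proportion alone, so this analysis cannot change it. That limits the consequence but does not supply the missing threshold.

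**Conclusion.** The point holds as a gap in specification. The secondary VAS TOST has no margin in VAS units, no stated choice between one limit and both, and no adjustment tied to it. With 43 v 43 and an assumed SD of change of 12 to 30 mm, the 90% half-width is about 4.3 to 10.6 mm. Plausible margins of 5 to 15 mm therefore span near-certain failure to likely success when there is no true difference: at SD 20, from 0.000 to 0.928 with both limits and from 0.313 to 0.965 with the lower limit. Failure of a clearly better device is conditional on a literal two-sided TOST.

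The case for baseline adjustment rests on removing baseline VAS differences under a stated model, with a precision gain of about 0 to 22% under the assumptions shown. It does not remove other historical-control bias. In the reference active arm, mean improvement ran from 35.1 points at 1 to 12 months of pain to 18.6 beyond 96 months, and pain duration is collected but is not on the covariate list. This should be corrected, as a matter affecting supportive evidence rather than the study's success criterion.

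**What to change.** Replace the bullet with: ANCOVA of VAS at study endpoint on group, with baseline VAS as covariate, using individual data from both studies; report the adjusted difference (dual-diode minus red only) with its 90% confidence interval. Then choose one of two options:

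1. **Non-inferiority verdict.** Before the data sets are merged, state and justify a margin in VAS mm, and decide only on the side where dual-diode is worse. Because lower endpoint VAS is better, that is the upper limit of the adjusted difference. Say how the direction is applied while the groups are masked, for example by reporting both limits and applying the rule at unmasking.
2. **No verdict.** Drop TOST and report the estimate and interval only.

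For option 1, the subjects needed per group (80% power, one-sided 0.05, no true difference, no baseline adjustment) at SD 15, 20 and 28 are 112, 198 and 388 for a 5 mm margin; 28, 50 and 97 for 10 mm; and 13, 22 and 44 for 15 mm. If a margin that can be justified is too small for 43 per group, option 2 is the more honest choice.

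The cost is wording. No new data are needed, since the statistician is to receive both data sets. The sponsor gives up the freedom to choose the margin later.
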